**REVISION HISTORY**

*This Revision History table is provided for the benefit of study team version control. If this table will not be useful to your team, you do not need to include it.*

Revision #	Version Date	Summary of Changes	Consent Change?

## 1.0 Study Summary

Study Title	Pilot Randomized Control Trial of Necrotizing Enterocolitis Screening using Abdominal Radiograph versus Bowel Ultrasound plus Abdominal Radiograph in Premature Neonates
Study Design	Pilot Randomized Controlled Trial
Primary Objective	To establish the feasibility and pilot the design and delivery of a diagnostic randomized controlled trial (RCT) of BUS for NEC evaluation.
Secondary Objective(s)	
 
• Explore whether the addition of BUS to the NEC diagnostic and monitoring pathway will change:             
 
1. The rates of medical versus surgical management
 
2. The days between NEC diagnosis and surgical intervention for those that need it
 
3. The days NPO for those that get medical management
 
 
 
• Develop a predictive model for NEC diagnosis
 
• Develop a predictive model for medical versus surgical management
 
• Explore the usefulness of serial fecal calprotectin levels as a predictive biomarker for NEC
 

Research Intervention(s)/Investigational Agent(s)	N/A
IND/IDE #	n/a
Study Population	Premature NICU babies under 32 weeks gestational age
Sample Size	160 subjects enrolled
Study Duration for Individual Participants	From enrollment until discharge or transfer from CMH
Study Specific Abbreviations/Definitions	NEC – Necrotizing Enterocolitis BUS – bowel ultrasound AXR – abdominal radiographs FC – fecal calprotectin NICU – Neonatal Intensive Care Unit CMH – Children's Mercy Hospital MRN – medical record number OSH – outside hospital LAR – legally authorized representative P/A/C – permission/assent/consent

	RCT – randomized controlled trial NPO – nothing by mouth VLBW – very low birth weight
--	---

## 2.0 Objectives

2.1 The overall primary objective is to establish the feasibility and pilot the design and delivery of a diagnostic randomized controlled trial (RCT) of BUS (bowel ultrasound) for NEC evaluation which will lead to a successful application for a larger, multi-center clinical trial in the future. This program of research is anticipated to have a significant positive impact in the timely and accurate diagnosis of NEC in preterm infants.

We plan to accomplish our overall objective for this project by pursuing the following specific aims:

1. Explore whether the addition of BUS to the NEC diagnostic and monitoring pathway will change:
  - (a) The rates of medical versus surgical management
  - (b) The days between NEC diagnosis and surgical intervention for those that need it
  - (c) The days NPO for those that get medical management
2. Develop a predictive model for NEC diagnosis
3. Develop a predictive model for medical versus surgical management

2.2 A secondary exploratory objective is to determine the usefulness of serial fecal calprotectin levels as a predictive biomarker of NEC. We hypothesize that tracking changes in fecal calprotectin levels from baseline can identify preterm infants with and without NEC.

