## 4.0 Study Endpoints

4.1 The primary endpoint for this study will be feasibility of recruitment into a diagnostic RCT and implementation of BUS intervention in infants with suspected NEC. Feasibility parameters to be assessed include recruitment, randomization, retention, and crossover. Recruitment will be measured as proportion of eligible infants who are enrolled, while randomization will be proportion of enrolled infants who develop NEC suspicion and undergo randomization. Retention will be defined as proportion of infants who complete the study. Crossover will be measured by proportion of infants randomized to standard of care who crossover to BUS arm. Successful implementation of intervention will be assessed by (1) proportion of properly completed BUS studies by sonographers; (2) proportion of adherence to standardized reporting template by radiologists, and (3) timeliness of stool collection in proximity to the BUS. For the secondary endpoint measures, time to achieve full enteral feeds will be defined as days to reach enteral feeds of 120mL/kg/day following suspension of feeds due to suspected NEC; and total antimicrobial days will be defined as days treated with empiric antibiotics due to suspected NEC. For the exploratory aim, the primary endpoint will be changes in serial fecal calprotectin levels and its association with NEC diagnosis.

[figure not shown]

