## 20.0 Data Management and Confidentiality

20.1 This is a pilot study only to evaluate feasibility of a larger clinical trial. We will use the pilot data in the future to perform a power analysis for the larger study.

20.2 We anticipate having to approach ~100 patients/year to achieve the 40 patients/year needed for our pilot study. We are assuming a NEC suspicion incidence rate of 50% and approximately 20% of parents/patients declining to consent for the study (e.g. 100 patients \* 80% consent rate \* 50% with NEC suspicion = 40 patients/year).

20.3 With a target of 80 patients randomized, we anticipate the enrollment period to last ~2 years. We will stop consenting patients as soon as we meet our desired enrollment.

20.4 A certificate of confidentiality will not be sought for this study.

20.5 Study data will be evaluated by the PI throughout the duration of the study for QA.

20.6 Patient information will be maintained in a REDCap application and will be housed within the CMH Data Center by the Division of Biomedical Informatics. The hosting server has an internal failover two-node cluster. The CMH Data Center is constantly staffed by qualified personnel and physical access is limited to authorized personnel. The

Center has optimized conditions for the servers and stabilized electrical supply. The database has a full backup. The database server is located inside the CMH corporate firewall. A person must have CMH system access to login. Additional security for the study patient database restricts access to only those persons specifically granted authorization by the Principle Investigator. It is possible for data to be downloaded from REDCap. Individuals who lack authority to see confidential data can download reports with non-identifiable data only. The core research group will have the ability to download sensitive fields and if such a download occurs, REDCap maintains a record of who, what, when, and to where copies of the database were imported.

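### Is the pilot too small, and NEC too loosely defined, for the two prediction models named in aims 2 and 3?

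*Combined protocol and SAP*

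**What the plan says.** Section 2.1 of the combined protocol and SAP introduces its list with "We plan to accomplish our overall objective for this project by pursuing the following specific aims". Aim 1 is to explore effects of adding bowel ultrasound (BUS) on management. Aims 2 and 3 are to develop a model for NEC diagnosis and, for the second model, "Develop a predictive model for medical versus surgical management". Section 1.0 lists both models as secondary objectives. Section 2.2 uses more cautious wording for the stool biomarker: "A secondary exploratory objective is to determine the usefulness of serial fecal calprotectin levels as a predictive biomarker of NEC".

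The sample size in section 1.0 is "160 subjects enrolled". Section 20.2 derives the yearly figure from approach, consent and suspicion rates ("We are assuming a NEC suspicion incidence rate of 50" per cent), and section 20.3 adds "With a target of 80 patients randomized, we anticipate the enrollment period to last ~2 years". Section 20.1 describes the study as a feasibility pilot and leaves the power analysis to the later trial.

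Under section 6.1, BUS is scheduled in one arm only and treating clinicians can see all imaging. Section 6 also says there is no blinding to BUS. Calprotectin results stay out of the medical record. Section 4.1 defines feasibility, feeding, antibiotic and calprotectin endpoints, but says nothing about how either model will be built.

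**The concern.** Three things look wrong on a first reading.

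- **Commitment against sample.** Aims 2 and 3 promise to develop models, without the exploratory label used elsewhere, yet the sample was never sized for modelling. The 50% in section 20.2 is a rate of suspicion. The text gives no rate of NEC diagnosis or surgery.
- **Unstated population and predictors.** The management model could be confined to infants with NEC, since aim 1(b) concerns "The days between NEC diagnosis and surgical intervention for those that need it". It could also take in every randomized infant, since section 4.1 says "total antimicrobial days will be defined as days treated with empiric antibiotics due to suspected NEC". If BUS findings are predictors, essentially only the BUS arm has them.
- **The NEC label.** The available text has no working case definition. If treating clinicians assign the diagnosis after seeing BUS, the test can enter the outcome it is meant to predict, and the outcome can mean different things in the two arms.

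At stake is the credibility of the models. With few events and an unpenalized fit, even uninformative predictors give an apparent AUC well above 0.5, and a label influenced by imaging could add to that.

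**Working it through.** **1. The plan's own figures.** 100 approached × 0.80 consenting × 0.50 with suspicion = 40 randomized per year. Over 2 years that is 80 randomized, with 100 × 0.80 × 2 = 160 enrolled. Sections 1.0, 13.1, 20.2 and 20.3 agree.

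**2. Assumptions, none of them in the documents.** 1:1 allocation (40 per arm); NEC in 20–50% of the 80 randomized; surgery in 20–50% of NEC; target shrinkage S = 0.9; Cox-Snell R² at 15%, 30% or 50% of its maximum.

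**3. Formula.** Supported parameters p = n(S − 1) ln(1 − R²/S). The maximum R² is 0.632, 0.726 and 0.750 at event rates of 20%, 35% and 50%.

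**4. Model using BUS findings (n = 40).** At a 50% event rate and half the maximum, R² = 0.375. Then p = 40 × (−0.1) × ln(1 − 0.375/0.9) = 40 × (−0.1) × (−0.539) = 2.16. At 30% and 15% of the maximum, p = 1.15 and 0.53. A 50% event rate gives the largest value, so under these settings 2.16 is the ceiling whatever the NEC rate. With 27 or 53 infants in the BUS arm, the ceiling is 1.46 or 2.86.

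**5. How firm is that ceiling?** It moves with the conventions chosen (n = 40, 50% event rate):

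| Setting | Parameters |
|---|---|
| S = 0.90, R² at 50% of maximum | 2.2 |
| S = 0.85, R² at 50% of maximum | 3.5 |
| S = 0.80, R² at 50% of maximum | 5.1 |
| S = 0.90, R² at 70% of maximum | 3.5 |
| 10 events per parameter (20 events) | 2.0 |
| 5 events per parameter (20 events) | 4.0 |

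**6. Other readings of the aims (S = 0.9).**

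| Model | Parameters |
|---|---|
| NEC diagnosis, no BUS, 80 randomized | 0.9–4.3 |
| NEC diagnosis, no imaging, 160 enrolled (16–40 cases) | 1.3–7.5 |
| Management, infants with NEC only | 0.2–2.2 |
| Management, all 80 randomized | 0.4–3.8 |
| Management with BUS, infants with NEC only | 0.1–1.1 |
| Management with BUS, all 40 in the BUS arm | 0.2–1.9 |

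The assumed rates give about 3 to 20 surgical infants in all (80 × 0.2 × 0.2 = 3.2; 80 × 0.5 × 0.5 = 20).

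**7. What a careless fit would show.** Mean apparent AUC from pure noise, over 2,000 near-unpenalized logistic fits per setting:

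| Infants / events | 5 predictors | 2 predictors |
|---|---|---|
| 40 / 8 | 0.743 | 0.642 |
| 40 / 20 | 0.696 | 0.615 |
| 80 / 16 | 0.670 | 0.599 |
| 80 / 40 | 0.636 | 0.578 |
| 28 / 10 | 0.744 | 0.639 |
| 160 / 28 | 0.625 | 0.575 |

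These describe a fit without penalization or optimism correction. The plan does not propose such a fit, nor does it exclude one.

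**8. The label, aim by aim.** For aim 3 the outcome is the management received, which can be observed directly. A NEC definition matters there only if the population is restricted to infants with NEC. For aim 2 the concern needs two conditions that the text does not state: clinicians assign the diagnosis, and imaging findings are predictors. Calprotectin results are kept from clinicians, so they cannot enter the label directly. The size of any effect is unknown.

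**The case for a change.** The strongest case for a change is that the aims make a promise the sample cannot keep. Section 2.1 says the overall objective is pursued through these aims and is meant to lead to an application for a larger trial. Overfitted models could therefore be presented as results of the study. Under the assumed rates, the management model confined to infants with NEC supports fewer than one parameter in 19 of 27 scenarios, and on all 80 randomized in 10 of 27. Calling both models exploratory, naming a few predictors, correcting for optimism and applying one BUS-free definition of NEC to both arms would cost little and would not touch patient care.

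Much of this stands. The arithmetic is right, and the available text does lack a population, predictors, validation and a NEC definition. But these are omissions. The scenario counts describe an assumed grid whose cells are not equally likely. The tightest figures rest on BUS predictors that the plan never specifies. The absence of a definition cannot be confirmed, because section 3.0 points to an appendix, section 6 to a reporting template, and the flow figure is not shown. The documents do not say that model performance feeds the later power analysis.

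**Conclusion.** No change to the plan is needed. The concern identifies missing detail. It does not show a stated method that would give a wrong answer. Section 20.1 says the study serves feasibility, and section 1.0 ranks both models as secondary, which is reason enough to read their results as exploratory despite the stronger verb.

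On size, a BUS-based model under 1:1 allocation supports roughly 2 parameters at S = 0.9 and half the maximum R², and about 0.5 to 5 across other reasonable conventions. A NEC model without BUS on the 80 randomized supports about 0.9 to 4.3. The management model is the most constrained, and under many assumed rates would amount to event counts and single-predictor associations. These figures rest on assumed NEC and surgery rates, allocation and R².

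The remaining choices can be made sensibly at analysis: population, unit where infants have repeat episodes, number of predictors given the observed events, penalization and optimism correction. Whether the NEC diagnosis absorbed BUS information can be handled when aim 2 is reported, and an unseen appendix may already hold the definition. The primary feasibility objective is unaffected.

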## 3.0 Background

Necrotizing enterocolitis (NEC) is the most common bowel disease in premature and low birth weight neonates. NEC is defined by the loss of mucosal integrity of the bowel wall enabling bacteria and other toxins to permeate into the bowel causing ischemia and necrosis which can lead to bowel perforation and sepsis (1, 2). NEC can result in substantial morbidity and mortality and prolonged hospital stay.

In the past, abdominal radiography has been scored on a standard scale that correlated with outcomes. Duke University Medical Center developed a standardized ten-point radiographic scale, the Duke Abdominal Assessment Scale (DAAS) (Appendix B) and was proven to be directly proportional to the severity of NEC on patients that underwent surgery (3, 4). Abdominal radiographs are assessed for gas pattern, bowel distention, location and features, pneumatosis (gas in bowel wall), portal venous gas, and pneumoperitoneum (free air in peritoneal cavity) to indicate the level of suspicion of NEC (3, 4). The use of abdominal radiographs is the most common assessment for suspected NEC in infants, however, there have been recent studies done on the utility of bowel ultrasound to aid in early diagnosis of NEC due to the ability to evaluate peristalsis, echogenicity and thickness of bowel wall, pneumatosis and the capability of doing color Doppler to evaluate blood perfusion(2). A University of Toronto study used ultrasound to assess bowel perfusion with color Doppler in neonates and found a correlation between absence of bowel wall perfusion and the increased severity of NEC on surgical pathology (5). Although there are similar signs found between abdominal radiography and bowel ultrasound, some of the more severe features

such as, pneumoperitoneum, were found to be more sensitive on bowel ultrasound, thus potentially leading to more definitive treatment (5). Currently, there is no good study evaluating whether the use of bowel ultrasound affects clinical outcomes in VLBW patients over the use of abdominal radiography alone.

The use bowel ultrasound has yet to be adopted in the setting of suspicion for NEC at our institution. This is primarily due to the lack of expertise of the ultrasound technologists, radiologists and clinicians. With literature dating back to 2005(5, 6) supporting the use of bowel ultrasound in diagnosis of severity of NEC, we would like to see if a regimen involving combined ultrasound and radiograph screening for NEC would make a difference in clinical outcomes (morbidity, mortality, and length of stay (LOS)) compared with radiograph screening alone.

Calprotectin is a protein found in the stool that, at elevated levels, indicates gastrointestinal inflammation. The addition of fecal biomarkers to the diagnostic work up for NEC also has promising impact. It has been suggested that fecal calprotectin levels obtained at the time of suspicion of NEC may be a useful noninvasive indicator to determine the severity of inflammation in the intestine and whether it is related to NEC or other forms of inflammation. (8) Correlation of the fecal biomarkers with findings on BUS may be helpful to more definitively diagnose NEC.

## 4.0 Study Endpoints

4.1 The primary endpoint for this study will be feasibility of recruitment into a diagnostic RCT and implementation of BUS intervention in infants with suspected NEC. Feasibility parameters to be assessed include recruitment, randomization, retention, and crossover. Recruitment will be measured as proportion of eligible infants who are enrolled, while randomization will be proportion of enrolled infants who develop NEC suspicion and undergo randomization. Retention will be defined as proportion of infants who complete the study. Crossover will be measured by proportion of infants randomized to standard of care who crossover to BUS arm. Successful implementation of intervention will be assessed by (1) proportion of properly completed BUS studies by sonographers; (2) proportion of adherence to standardized reporting template by radiologists, and (3) timeliness of stool collection in proximity to the BUS. For the secondary endpoint measures, time to achieve full enteral feeds will be defined as days to reach enteral feeds of 120mL/kg/day following suspension of feeds due to suspected NEC; and total antimicrobial days will be defined as days treated with empiric antibiotics due to suspected NEC. For the exploratory aim, the primary endpoint will be changes in serial fecal calprotectin levels and its association with NEC diagnosis.

[figure not shown]

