## 6.0 Procedures Involved

6.1 Experienced research coordinators will screen for potentially eligible infants daily. NICU staff may notify someone from the study team about potential subjects. Infants successfully enrolled in the study will be clearly identified by signage at the bedside and updated lists in the work room. All enrolled subjects will have a baseline fecal calprotectin level obtained at the time of enrollment or with next stool. If an enrolled infant develops concern for NEC (as determined clinically by treating neonatologist), a sealed envelope will be opened to reveal to which arm the infant is randomized: **(A) AXR only (standard of care)** or **(B) AXR and BUS (intervention)**.

*Intervention.* Infants randomized to the **AXR only arm** will obtain an AXR as per standard of care (see **Figure**). Repeat AXR, if any, will be left to the discretion of the treating neonatologist. In this arm, no BUS study will be performed *unless* the attending neonatologist decides it is clinically indicated. This situation is expected to be exceedingly rare, as BUS is not part of the standard of care for NEC evaluation. Infants randomized to the **AXR and BUS arm** will also get an AXR, with repeat AXR left to the discretion of the treating neonatologist. In addition to this standard of care, infants randomized to this arm will receive a BUS as the intervention. This BUS will be ordered at the same time as the initial AXR and will be performed within six hours of the order being placed. Since CMH has overnight and weekend sonographers, BUS can be done performed 24/7. An additional BUS and fecal calprotectin level will be performed once every 24-hours until clinical suspicion is no longer warranted. Enrolled patients who may undergo multiple “suspected NEC” encounters during the course of their admission will remain in the same arm throughout the study.

**Figure:** Flow diagram of study following randomization.

Management. All AXR and BUS exams will be interpreted by board-certified pediatric radiologists, and all imaging results will be available for clinicians to review as part of the subject's medical record. Fecal calprotectin levels will be documented in the patient's research data, but not included in the subject's medical record. All laboratory tests and treatment, including antibiotics or bowel rest, will be left to the discretion of the treating neonatologist. Participation in the study will end at the time of discharge or transfer.

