BUS performance and interpretation. US performance and interpretation will be performed by a sonographer and radiologist, respectively, as per standard clinical work-flow. All BUS results will be available to the study team (i.e. no blinding). Variability in performance of US by sonographers will be minimized by pre-study training and quick reference cards in each US machine as detailed above. Likewise, variability in US interpretation will be minimized by the pre-study training as well as the use of a standardized template for reporting US results (see **Appendix**). All study US exams will be over-read by the study radiologists to ensure accurate interpretation. In cases of differences in their readings, final interpretation will be made by the study radiologists and these results will be communicated to the clinical team.

Fecal calprotectin measurement. Stool will be collected from a diaper following study enrollment regardless of rate of feeds. We will do an additional collection of stool after five weeks of life to get a baseline calprotectin level. "Baseline" is defined as an infant who is greater than or equal to five weeks of age and is tolerating full enteral feeds of at least 120 mL/kg/day. All stool samples will be collected by the NICU nurse or study staff. Stools can be stored for up to 72 hours if needed and then processed using the Fecal Calprotection High Range Quantitative Quantum Blue assay. All results will be recorded in Redcap. If a baby develops a concern for NEC, the next three stool samples at least a day apart will be collected for FC analyzation. An additional stool sample will also be collected at the resolution of NEC watch, which is defined by tolerance of  $\geq 120$ mL/kg/day of enteral feeds for at least two days. Infants who have repeated concern for NEC will again have the first three stool samples collected with each event, with another stool also collected at resolution of NEC. The stool samples will be kept suspended in a buffer in a test tube for the duration of the study in the event a sample needs to be retested.

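### The exploratory calprotectin endpoint names only change from baseline; modelling the level at suspicion with a pre-event baseline as covariate would do at least as well, whatever the unknown correlation

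*Combined protocol and SAP*

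**What the plan says.** The Study Summary (1.0) words the objective broadly: "Explore the usefulness of serial fecal calprotectin levels as a predictive biomarker for NEC". Section 2.2 narrows it to a hypothesis that "tracking changes in fecal calprotectin levels from baseline can identify preterm infants with and without NEC". Section 4.1 then sets the endpoint for this aim: "the primary endpoint will be changes in serial fecal calprotectin levels and its association with NEC diagnosis". The Background (3.0) argues from a different quantity, noting a suggestion that "fecal calprotectin levels obtained at the time of suspicion of NEC may be a useful noninvasive indicator".

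On sampling, section 6.1 opens with "All enrolled subjects will have a baseline fecal calprotectin level obtained at the time of enrollment or with next stool". Later, under fecal calprotectin measurement, it calls for a further stool after five weeks of life and says that baseline "is defined as an infant who is greater than or equal to five weeks of age", with full enteral feeds also required. Once there is concern for NEC, "the next three stool samples at least a day apart will be collected for FC analyzation", and one more is taken at resolution. All results go into the study database.

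No analysis model, transformation, cut-off or comparison group is given for calprotectin.

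**The concern.** The endpoint sentence is the only specification an analyst has for this aim. Read with section 2.2, it points to the suspicion value minus the baseline value. A difference gives the baseline a fixed weight of -1, whether or not baseline tracks the later value. If the two are weakly correlated, subtraction adds more noise than it removes, and a marker that is informative at suspicion can look poor. The quantity that motivates the aim in the Background has no named endpoint.

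At stake is what the pilot carries forward. Section 20.1 says that its data will feed the power analysis of the larger study. A change-only result could drop a useful marker or hand on an effect size diluted by baseline variation.

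**Working it through.** **Inputs from the documents.** Section 20.2 states "We are assuming a NEC suspicion incidence rate of 50% and approximately 20% of parents/patients declining to consent for the study". This reproduces the plan's figures: 100 × 0.80 × 0.50 = 40 randomized per year; over two years 2 × 40 = 80 randomized and 2 × 100 × 0.80 = 160 enrolled. Stools after concern exist only for infants with concern, so about 80 infants can contribute a suspicion value.

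**Inputs not in the documents (assumed).** Log values; equal SDs (set to 1) at baseline and suspicion; no baseline difference between NEC and non-NEC; NEC raises the suspicion value by d = 0.8 SD; r from 0 to 0.9; NEC in 12, 16, 20 or 40 of the 80; one episode per infant.

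**Variance of each score.** Level: v = 1. Change: v = 1 + 1 − 2r = 2(1 − r). Level adjusted for baseline: v = 1 − r². The difference between the last two is 2(1 − r) − (1 − r²) = (1 − r)², which is never negative. So the adjusted level is at least as good as change at every r. Change loses to the level alone when 2(1 − r) > 1, that is r < 0.5. With unequal SDs the condition is r < SD(baseline) / (2 × SD(suspicion)).

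**Discrimination.** AUC = Φ(d / √(2v)). For example, change at r = 0.3: Φ(0.8 / √2.8) = Φ(0.478) = 0.684.

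| r | change | level | level + baseline |
|---|---|---|---|
| 0 | 0.655 | 0.714 | 0.714 |
| 0.3 | 0.684 | 0.714 | 0.723 |
| 0.5 | 0.714 | 0.714 | 0.743 |
| 0.7 | 0.767 | 0.714 | 0.786 |
| 0.9 | 0.897 | 0.714 | 0.903 |

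Other effect sizes at r = 0.3, in the same order: d = 0.5 gives 0.617 / 0.638 / 0.645; d = 1.0 gives 0.725 / 0.760 / 0.771.

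**If the groups already differ at baseline by d0.** Change equals the level when r = 1 − ((d − d0)/d)² / 2. With NEC infants 0.3 SD higher: 1 − (0.5/0.8)² / 2 = 0.80. With NEC infants 0.3 SD lower: 1 − (1.1/0.8)² / 2 = 0.05.

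**Power.** Power = Φ(d / √(v(1/n1 + 1/n0)) − 1.96), two-sided 5%. With 16 NEC and 64 non-NEC, √(1/16 + 1/64) = 0.2795, so the level alone gives Φ(2.86 − 1.96) = 82%.

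| r | change | level | level + baseline |
|---|---|---|---|
| 0.1 | 57% | 82% | 82% |
| 0.3 | 68% | 82% | 85% |
| 0.7 | 96% | 82% | 98% |

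Other NEC counts at r = 0.3, in the same order: 12 of 80, 58 / 72 / 76%; 20 of 80, 75 / 87 / 90%; 40 of 80, 86 / 95 / 96%.

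**Price of the extra coefficient.** The AUCs above treat the weights as known. A simulation with weights fitted on 80 infants (4,000 runs per setting, d = 0.8) gave these out-of-sample AUCs for change / level / level + baseline:

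- 12 NEC cases: 0.646 / 0.711 / 0.695 at r = 0; 0.678 / 0.712 / 0.705 at r = 0.3; 0.767 / 0.712 / 0.774 at r = 0.7.
- 20 NEC cases: 0.651 / 0.714 / 0.701 at r = 0; 0.683 / 0.714 / 0.711 at r = 0.3; 0.767 / 0.714 / 0.778 at r = 0.7.
- 40 NEC cases: 0.654 / 0.714 / 0.705 at r = 0; 0.683 / 0.714 / 0.714 at r = 0.3; 0.767 / 0.714 / 0.780 at r = 0.7.

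The fitted joint score was above change at every r tried. Against the level alone it lost 0.009 to 0.016 at r = 0 and gained from r = 0.5 upward.

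**The case against.** The strongest reply is that the documents never specify subtraction. Changes in serial levels could mean a trajectory or a repeated-measures analysis of the several stools collected, and the fixed weight of -1 is then an inference. This stands, and the point is conditional on a simple difference. It does not remove the need to name the analysis.

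A reader might infer that the plan throws the level away. It does not: every result is recorded, the stated objective speaks of levels, and nothing bars the level from the planned predictive model for NEC diagnosis. The level is missing only from the named endpoint. Nor is testing change a contradiction of the Background; it is a legitimate hypothesis.

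A reader might also infer that change is the poorer marker. The documents give no correlation to support that. Above r = 0.5, on equal SDs and no baseline difference, change beats the level alone, and the break-even shifts widely with a baseline difference. An enrollment stool taken at any feeding rate, with no limit on the time to suspicion, makes a low r plausible but does not establish it.

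Finally, adjustment is not free. At low r the joint model is slightly worse than the level alone when weights are fitted on few cases. And under the five-week definition, an infant suspected earlier would have only a post-event baseline to adjust for. Both stand; the second affects the change score equally.

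**Conclusion.** The point holds as an improvement to an exploratory aim. Compared with a simple difference, the joint model gains 0.059 in AUC at r = 0 (0.714 − 0.655), 0.039 at r = 0.3, 0.019 at r = 0.7 and 0.006 at r = 0.9, at d = 0.8. That it is no worse than change does not depend on r; the size of the gain does, and it nearly vanishes when r is high. The ranking of change against the level alone cannot be settled from the documents. All magnitudes rest on the assumed effect, SDs, baseline equality and NEC counts. The trial's feasibility conclusion is untouched, and because raw levels are kept, the analysis remains possible with the data planned.

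**What to change.** 1. Reconcile the two baseline definitions in section 6.1 (enrollment or next stool; at least five weeks of age on full feeds), so that the baseline used in this analysis is a sample taken before the episode of concern.
2. In section 4.1, specify the main exploratory analysis as NEC diagnosis on log calprotectin in the first stool after concern, with log pre-event baseline as a covariate.
3. Report the level alone and the change from baseline alongside. The joint model contains change as the case of equal and opposite coefficients, so the section 2.2 hypothesis stays testable. Infants without a usable baseline remain in the level-only analysis.
4. Report the observed r, which the larger study will need.

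The cost is wording and one extra coefficient, with no additional stools or infants. The downside is about 0.01 to 0.02 in AUC against the level alone at low r when NEC cases are few, which is why the level-only result should be shown too.
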